4.2 Eligibility Criteria

4.2.1 **Inclusion Criteria**

Patients must meet all the following inclusion criteria to be eligible for enrollment into the study:

- 1) Signed informed consent approved by the Institutional Review Board (IRB). Patients must sign an authorization for the release of their protected health information;
- 2) Age ≥ 18 years;
- 3) Life expectancy > 12 weeks;
- 4) Present with histologically confirmed intracranial (supratentorial) unmethylated MGMT promotor status GBM (WHO Grade IV astrocytoma) with an MGMT status that has been confirmed by validated PCR or validated alternative genomic analysis;
- 5) Have undergone maximal or subtotal surgical resection of their tumor and within 6 weeks of surgery commenced radiation and then received at least 75% of planned treatment with XRT/TMZ or XRT only (if clinically indicated), which consists of XRT by external beam to a partial brain field in daily fractions of 2.0 Gray (Gy), to a planned total dose to the tumor of 60.0 Gy, in conjunction with TMZ oral QD 75 mg/m² in accordance with the Stupp regimen;
- 6) Karnofsky Performance Status (KPS) ≥ 70;
- 7) Cranial magnetic resonance imaging (MRI) must have been performed within 14 days prior to or on the day of the Enrollment/Week 1 Visit;
- 8) Stable or decreasing corticosteroid dose within 7 days prior to the first dose;
- 9) Adequate bone marrow/hematological function within 14 days prior to Day 1:
 - White blood cell count (WBC) > 3,000/µL, absolute neutrophil count > 1,500/mm³;
 - Platelet count of > 100,000/mm³;
 - Hemoglobin > 10 mg/dL;
 - Eligibility level for hemoglobin may be reached by transfusion;
- 10) Adequate liver function within 14 days prior to Day 1:
 - Total bilirubin ≤ 1.5 x ULN;
 - AST and ALT ≤ 2.5 x ULN;
- 11) Adequate renal function within 14 days prior to Enrollment/Week 1 Visit:
 - Creatinine ≤ 1.5 mg/dL;
 - Urine dipstick for proteinuria < 2+. Patients discovered to have ≥ 2+ proteinuria on dipstick urinalysis should undergo a 24-hour urine collection and must demonstrate ≤ 1.0 g of protein in 24 hours: OR
 - Urine protein/creatinine ratio ≤ 1.0;
- 12) International normalized ratio (INR) or prothrombin time (PT) (secs) and activated partial thromboplastin time (aPTT) within 7 days prior to Enrollment:
 - ≤1.5 x ULN (except for patients receiving anticoagulation therapy) in the absence of therapeutic intent to anti-coagulate the patient;

Version: Amendment 4 Date: 31 Mar 2020

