Abnormal values in AST and/or ALT concurrent with abnormal elevations in total bilirubin that meet the criteria outlined below in the absence of other causes of liver injury are considered potential cases of drug-induced liver injury (potential Hy's Law cases) and should always be considered important medical events.

The threshold of laboratory abnormalities for a potential case of drug-induced liver injury depends on the patient's individual baseline values and underlying conditions. Patients who present with the following laboratory abnormalities should be evaluated further to definitively determine the etiology of the abnormal laboratory values:

- Patients with AST or ALT and total bilirubin baseline values within the normal range who subsequently present with AST or ALT ≥ 3 x ULN concurrent with a total bilirubin ≥ 2 x ULN with no evidence of hemolysis and an alkaline phosphatase $\leq 2 \times \text{ULN}$ or not available;
- For patients with preexisting ALT OR AST OR total bilirubin values above the upper limit of normal, the following threshold values should be used in the definition mentioned above:
- For patients with pre-existing AST or ALT baseline values above the normal range: AST or ALT \geq 2 x the baseline values and \geq 3 x ULN, or \geq 8 x ULN (whichever is smaller);
- For patients with pre-existing values of total bilirubin above the normal range: Total bilirubin increased by one time the ULN $or \ge 3$ x the lower limit of normal (whichever is smaller).

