If able to do so, the patient should return to the investigational site and be evaluated as soon as possible, preferably within 48 hours from awareness of the abnormal results. This evaluation should include laboratory tests, detailed history and physical assessment. For oncology studies, the possibility of hepatic neoplasia (primary or secondary) should be considered. In addition to repeating AST and ALT, laboratory tests should include albumin, creatine kinase, total bilirubin, direct and indirect bilirubin, GGT, PT/INR, and alkaline phosphatase. A detailed history, including relevant information, such as review of ethanol, acetaminophen, recreational drug and supplement consumption, family history, occupational exposure, sexual history, travel history, history of contact with a jaundiced patient, surgery, blood transfusion, history of liver or allergic disease, and work exposure, should be collected. Further testing for acute hepatitis A, B, or C infection and liver imaging (e.g., biliary tract) may be warranted. All cases confirmed on repeat testing as meeting the laboratory criteria defined above, with no other cause for liver function test (LFT) abnormalities identified at the time should be considered potential Hy's Law cases irrespective of availability of all the results of the investigations performed to determine etiology of the abnormal LFTs. Such potential Hy's Law cases should be reported as SAEs.

Version: Amendment 4 Date: 31 Mar 2020

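### Section 5.5.1: for patients with raised baseline bilirubin, the 3 x LLN alternative can be met by an unchanged baseline value, so the bilirubin part of the potential Hy's Law definition may do no work

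*Combined protocol and SAP*

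**What the plan says.** Section 5.5.1 of the protocol (Drug Induced Liver Injury, under 5.5) defines laboratory criteria for a potential Hy's Law case.

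- **Normal baseline.** The criteria apply to patients "who subsequently present with AST or ALT ≥ 3 x ULN concurrent with a total bilirubin ≥ 2 x ULN", with no hemolysis and with alkaline phosphatase no more than 2 x ULN or unavailable.
- **Raised baseline.** For patients with a raised ALT, AST or bilirubin at entry, "the following threshold values should be used in the definition mentioned above". The definition keeps its structure and only the limits change.
- **Raised baseline bilirubin.** The bullet begins "For patients with pre-existing values of total bilirubin above the normal range". Its first alternative is "Total bilirubin increased by one time the ULN". Its second is a value of at least 3 "x the lower limit of normal (whichever is smaller").
- **Consequence.** The next step covers "All cases confirmed on repeat testing as meeting the laboratory criteria defined above", with no other cause identified at the time. It ends: "Such potential Hy's Law cases should be reported as SAEs".

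Inclusion criterion 10 (section 4.2.1) allows "Total bilirubin ≤ 1.5 x ULN". The covered patients are therefore those entering above 1.0 and up to 1.5 x ULN.

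**The concern.** A raised-baseline rule should ask for a change from the patient's own starting point, and section 5.5.1 itself says that the threshold depends on individual baseline values. The second alternative contains no baseline term. It is also the only threshold in the section tied to the lower limit of normal; every other one is a multiple of ULN or of baseline. The words are written out in full, so this is not a symbol lost in conversion.

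Because the smaller alternative governs, a low second alternative disables the first. At stake is a trigger for SAE reporting. Section 5.12.1 requires notification within 24 hours, and SAEs are a secondary safety endpoint (section 4.5.2) in a study of about 32 patients whose primary objective is safety. Table 1 allows central or local testing, so a limit based on LLN could also differ between laboratories across the 5-7 sites.

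**Working it through.** The plan states no figure to reproduce. The check is algebra on the thresholds, in units of ULN.

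**Inputs**
- Baseline bilirubin b: above 1.0 and up to 1.5 (sections 5.5.1 and 4.2.1).
- First alternative: b + 1 (section 5.5.1).
- Second alternative: 3 x LLN = 3/k, where k = ULN/LLN (section 5.5.1).
- Normal-baseline limit: 2 (section 5.5.1).
- k is not given in the protocol. It is an assumption, varied from 1.5 to 12.

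**Absolute-level reading.** The operative threshold is min(b + 1, 3/k).

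1. Since b > 1, the first alternative exceeds 2; over the eligible range it runs from just above 2.0 to 2.5.
2. The second alternative is at most 2 when 3/k ≤ 2, that is k ≥ 1.5. From there on it is always the smaller, and the one-ULN rise never operates.
3. The limb is met at baseline when b ≥ 3/k. With b > 1, this holds for every covered patient once 3/k ≤ 1, that is k ≥ 3.

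| k = ULN/LLN | 3 x LLN, in ULN | Covered patients already at or above it at baseline |
|---|---|---|
| 1.5 | 2.0 | none |
| 2 | 1.5 | only those at b = 1.5 |
| 2.5 | 1.2 | those with b from 1.2 to 1.5 |
| 3 | 1.0 | all |
| 4 | 0.75 | all |
| 6 | 0.50 | all |
| 12 | 0.25 | all |

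In assumed laboratory units with ULN 1.2 mg/dL, an LLN of 0.1, 0.2, 0.3 or 0.4 mg/dL gives 3 x LLN = 0.3, 0.6, 0.9 or 1.2 mg/dL. Dividing by 1.2 gives 0.25, 0.50, 0.75 or 1.00 x ULN. A covered patient starts above 1.2 mg/dL in each case.

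**Incremental reading.** If the word for a rise governs both alternatives, the required rise is min(1, 3/k).

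1. An unchanged value does not qualify (unless LLN is 0).
2. For k > 3, 3/k < 1, so the 3 x LLN alternative again overrides the one-ULN rise.
3. With ULN 1.2 and LLN 0.1, 0.2 or 0.3 mg/dL, the rise needed is 0.3, 0.6 or 0.9 mg/dL, against 1.2 mg/dL under the first alternative.

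**Which reading.** The second alternative carries its own greater-than-or-equal sign. The parallel AST/ALT bullet uses the same construction with an absolute multiple of ULN, again with the smaller governing. Both features favour the absolute-level reading but do not settle it.

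**The case against.** A reader might infer that in these patients a transaminase rise by itself automatically becomes a Hy's Law SAE. The documents do not support that. The case must still show AST/ALT at its own threshold, no hemolysis, and alkaline phosphatase no more than 2 x ULN or unavailable. It must be confirmed on repeat testing with no other cause identified. An investigator who knows why bilirubin was raised at entry may be able to exclude the case. These filters stand, but none of them restores a requirement that bilirubin change. The section's opening reference to abnormal bilirubin does not restore it either: it defers to the criteria below it, and a baseline above ULN is already abnormal.

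Section 4.9.1 limits the reach further. Bilirubin must be within normal institutional limits before each next cycle, and a patient who cannot be retreated within 2 weeks should be removed. A patient whose bilirubin stays above ULN should therefore not start Cycle 2. The open window is mainly Cycle 1, any delay, and the 28-day reporting period in section 5.2. This stands.

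The incremental reading is possible, and on it the limb is not already met at baseline. That also stands, although the first alternative is still overridden when ULN exceeds 3 x LLN.

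Finally, the error is cautious: it adds cases and misses none. The laboratory summaries in section 6.3.5 and the listings in section 6.3.3 would help show that bilirubin had not moved. The most frequent drug-attributed events reported from the 47-patient phase 1 study (Risk/Benefit Analysis) do not include transaminase or bilirubin elevations, so the number of affected patients may be zero. This limits the weight of the point but does not make the threshold correct.

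**Conclusion.** The bilirubin criterion for raised-baseline patients is wrong as written. On the absolute-level reading, with ULN at least 3 x LLN, all covered patients satisfy it before the first dose. With a ratio of 2 to 2.5, some do, and the threshold of 1.5 to 1.2 x ULN is still below the 2 x ULN asked of normal-baseline patients. On the incremental reading some rise is needed, but the one-ULN alternative remains inoperative when ULN exceeds 3 x LLN. That an SAE trigger allows two materially different readings is itself a reason to correct it.

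The result rests on the assumed reference range, because the protocol gives none. A reader might also translate one false case into 1/32, about 3% of the study. That is only what one case would weigh; the documents give no basis for estimating how often it would happen, and they do not support a claim that the drug's hepatic risk will be misstated. What is supported is a route to over-reporting potential Hy's Law SAEs in a small group over a limited window. The DLT definition, the primary endpoint and the sample size are unaffected.

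**What to change.** The sponsor's safety group should confirm what the second alternative in the last bullet of the threshold list in section 5.5.1 was meant to say. It should then reconcile that alternative with the one-ULN rise in the same bullet and with the 2 x ULN criterion for normal-baseline patients. The corrected sentence should make clear whether each alternative is a level or a rise, and an unchanged baseline value should not be able to satisfy it. No particular limit is proposed here; that choice belongs to the safety group.

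The same wording should go into the SAE reporting instructions. The cost is one phrase in the next amendment and in those instructions, with no new data or visits.

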5.6 Hospitalization

AEs reported from studies associated with hospitalization or prolongations of hospitalization are considered serious. Any initial admission (even if less than 24 hours) to a healthcare facility meets these criteria. Admission also includes transfer within the hospital to an acute/intensive care unit (e.g., from the psychiatric wing to a medical floor, medical floor to a coronary care unit, neurological floor to a tuberculosis unit).

Protocol Number: NVGN-0084-201

IND Number: 112.608

Hospitalization does not include the following:

- Rehabilitation facilities:
- Hospice facilities;
- Respite care (e.g., caregiver relief);
- Skilled nursing facilities;
- · Nursing homes;
- Routine emergency room admissions;
- Same day surgeries (as outpatient/same day/ambulatory procedures),
- Hospitalization or prolongation of hospitalization in the absence of a precipitating, clinical AE is not in itself an SAE. Examples include:
 - Admission for treatment of a preexisting condition not associated with the development of a new AE or with a worsening of the preexisting condition (e.g., for work-up of persistent pre-treatment lab abnormality);
 - Social admission (e.g., patient has no place to sleep);
 - o Administrative admission (e.g., for yearly physical exam);
 - Protocol-specified admission during a study (e.g., for a procedure required by the study protocol);
 - Optional admission not associated with a precipitating clinical AE (e.g., for elective cosmetic surgery);
 - Hospitalization for observation without a medical AE;
 - Pre-planned treatments or surgical procedures should be noted in the baseline documentation for the entire protocol and/or for the individual patient,
 - Admission exclusively for the administration of blood products,
 - Diagnostic and therapeutic non-invasive and invasive procedures, such as surgery, should not be reported as AEs. However, the medical condition for which the procedure was performed should be reported if it meets the definition of an AE. For example, an acute appendicitis that begins during the AE reporting period should be reported as the AE, and the resulting appendectomy should be recorded as treatment of the AE.

5.7 Adverse Event Severity Assessment

Patients will be evaluated for safety if they have received any treatment. Adverse events and other symptoms will be graded according to National Cancer Institute's Common Toxicity Criteria for Adverse Events version 4.03 (CTCAE v4.03).

Table 2: CTCAE v4.03 Grading

Grade	Clinical Description of Severity
0	No change from normal or reference range
	(This grade is not included in the Version 4.03 document but may be used in certain
	circumstances.)
1	Mild
2	Moderate
3	Severe
4	Life-threatening or disabling
5	Death related to AE

Version: Amendment 4 Date: 31 Mar 2020

5.8 Causality Assessment

The Investigator's assessment of causality must be provided for all AEs (serious and non-serious); the Investigator must record the causal relationship in the CRF, as appropriate, and report such an assessment in accordance with the serious adverse reporting requirements if applicable.

Protocol Number: NVGN-0084-201

IND Number: 112.608

The causality assessment categorization will be:

- Unrelated: If there is no relationship and/or other factors (medicinal products or underlying disease) prove an explanation. Clearly due to extraneous causes;
- Unlikely related: If the event occurs within an improbable temporal relationship, and/or in which other factors provide a more plausible explanation;
- Possibly related: If the event occurs within a reasonable time sequence, but can also be
 explained by concurrent disease, medicinal products, or chemicals and investigational
 product causality is one of other causes for the described clinical event;
- Probably related: If the event occurs within a reasonable time sequence, was unlikely to be attributed to other factors (concurrent disease, medicinal products);
- Related: If the event occurs within a reasonable time sequence and could cannot be attributed to other factors (e.g., concurrent disease, chemicals, confounding drug administration must be absent.

An Investigator's causality assessment is the determination of whether there exists a reasonable possibility that the investigational product caused or contributed to an AE; generally, the facts (evidence) or arguments to suggest a causal relationship should be provided. If the Investigator does not know whether the investigational product caused the event, then the event will be handled as "related to investigational product" for reporting purposes, as defined by the sponsor (see Section 5.12).

If the Investigator's causality assessment is "unknown but unrelated to investigational product", this should be clearly documented on study records. In addition, if the Investigator determines an SAE is associated with study procedures, the Investigator must record this causal relationship in the source documents and CRF, as appropriate, and report such an assessment in accordance with the SAE reporting requirements, if applicable.

5.9 Exposure During Pregnancy

Patients who become pregnant during the study period (up to 28 days after receiving the last investigational product dose) must not receive additional doses of investigational product and should be withdrawn from the study.

Patients should be instructed to notify the Investigator if it is determined after completion of the study that they became pregnant either during the study or within one month (minimum 28 days) after receiving the last investigational product dose.

If a pregnancy occurs within 28 days of dosing, the pregnancy should be followed to term, any premature terminations reported, and the health status of the mother and child including date of delivery and the child's gender and weight should be reported to Kazia Therapeutics Limited after delivery. The mother may freely choose to terminate the pregnancy as her own decision. Neither the sponsor nor Investigators should influence this decision in any way. Similarly, neither the Investigators nor sponsor have the right to intervene or influence this decision and any ensuing procedures. If this occurs, the termination of pregnancy should be considered an elective surgical procedure and any associated AEs attributed accordingly.

If the outcome of the pregnancy meets the criteria for an SAE (i.e., ectopic pregnancy, spontaneous abortion, intrauterine fetal demise, neonatal death, or congenital anomaly [in a live born, a terminated fetus, an intrauterine fetal demise, or a neonatal death]), the Investigator should follow the procedures for reporting SAEs.

Additional information about pregnancy outcomes that are reported as SAEs follows:

Spontaneous abortion includes miscarriage and missed abortion;

Version: Amendment 4 Date: 31 Mar 2020

Neonatal deaths that occur within 1 month of birth should be reported, without regard to
causality, as SAEs. In addition, infant deaths after 1 month should be reported as SAEs when
the Investigator assesses the neonatal death as related or possibly related to exposure to
investigational product.

Protocol Number: NVGN-0084-201

IND Number: 112.608

5.10 Withdrawal Due to Adverse Events

Withdrawal due to AE should be distinguished from withdrawal due to other causes, according to the definition of AE noted earlier, and recorded on the appropriate AE CRF page.

When a patient withdraws due to an SAE, the SAE must be reported in accordance with the reporting requirements defined in Section 5.12.

5.11 Eliciting Adverse Event Information

The Investigator is to report all directly observed AEs and all AEs spontaneously reported by the study patient. In addition, each study patient will be questioned about AEs.

5.12 Reporting Requirements

Each AE is to be assessed to determine if it meets the criteria for SAEs. If an SAE occurs, expedited reporting will follow local and international regulations, as appropriate.

5.12.1 Serious Adverse Event Reporting Requirements

If an SAE occurs, Kazia Therapeutics Limited, or its delegated representative, is to be notified within 24 hours of Investigator awareness of the event.

In particular, if the SAE is fatal or life-threatening, notification must be made immediately to Kazia Therapeutics Limited, or its delegated representative, irrespective of the extent of available AE information. This timeframe also applies to additional new information (follow-up) on previously forwarded SAE reports as well as to the initial and follow-up reporting of exposure during pregnancy and exposure via breastfeeding cases.

In the rare event that the Investigator does not become aware of the occurrence of an SAE immediately (e.g., if an outpatient study patient initially seeks treatment elsewhere), the Investigator is to report the event within 24 hours after learning of it and document the time of his/her first awareness of the AE.

For all SAEs, the Investigator is obligated to pursue and provide information to Kazia Therapeutics Limited in accordance with the timeframes for reporting specified above. In addition, an Investigator may be requested by Kazia Therapeutics Limited to obtain specific additional follow-up information in an expedited fashion. This information collected for SAEs is more detailed than that captured on the AE CRF and must be provided on an additional CRF for collection of detailed SAE information. Where the same data are collected, the forms must be completed in a consistent manner. For example, the same AE term should be used in all occasions this AE is referenced. AEs should be reported using concise medical terminology. In general, information to be provided will include a description of the AE in sufficient detail to allow for a complete medical assessment of the case and independent determination of possible causality. Information on other possible causes of the event, such as concomitant medications and illnesses must be provided. In the case of a patient's death, a summary of available autopsy findings must be submitted as soon as possible to Kazia Therapeutics Limited or its designated representative.

Information should be forwarded to the CRO's Pharmacovigilance group via the following e-mail address:

[contact]

The IRB must be informed if the SAE, in the opinion of Kazia Therapeutics Limited or the Investigator, is likely to affect the safety of the patients or the conduct of the study.

Version: Amendment 4 Date: 31 Mar 2020

Protocol Number: NVGN-0084-201 IND Number: 112.608

